# 14.3.7 Analysis of patient-reported outcomes

HESD score (weekly average) and HESD scores for itch, pain, cracking, redness, dryness, flaking (weekly average) will be summarised at each nominal week from baseline up to Week 36.

Page 84 of 121

A ≥4-point reduction from parent baseline of HESD score (weekly average), HESD scores for itch and pain (weekly average) respectively, will be summarised at each nominal week. Subjects who discontinue treatment with IMP prior to Week 36, initiate rescue treatment, or withdraw from the trial, whichever comes first, will be imputed as non-responders-.

HEIS score, HEIS (each individual domain) score, DLQI score, EQ-5D-5L visual analogue score, EQ-5D-5L index score, and WPAI:CHE (each individual domain) score, will be summarised at the scheduled visits where the assessments are performed from baseline up to Week 36.

# 14.3.8 Analysis of safety

The analysis of safety will be based on the safety analysis set.

#### 14.3.8.1 Adverse events

AEs will be coded during the course of the trial according to Medical Dictionary for Regulatory Activities (MedDRA). AEs will be presented by preferred term and primary system organ class (SOC).

AEs with onset after baseline visit will be considered treatment-emergent. AEs reported as ongoing at baseline in this trial will be reported as medical history. Any worsening of an ongoing AE after baseline visit will be recorded as a new AE in this trial. In each of the tabulations, AEs will be defined by MedDRA preferred terms within primary SOC. New AEs recorded after end of trial will be presented in a listing.

AEs will be summarised in terms of the number of subjects with at least 1 event, the percentage of subjects with at least 1 event, the number of events, and the event rate per 100 person years of observation time.

Related AEs are defined as AEs for which the investigator has not described the causal relationship to IMP as 'not related'.

An overall summary presenting any treatment-emergent AEs, deaths, SAEs, premature discontinuations from IMP and/or withdrawals from the trial due to AEs, treatment-related AEs, and severe AEs will be given.

Tabulations by SOC and preferred term will be presented for all AEs, SAEs, related AEs, AESIs, AEs leading to withdrawal from trial, and AEs leading to permanent discontinuation of IMP. In addition, all AEs will be presented by severity and causal relationship to IMP,

Page 85 of 121

respectively. If an AE worsens in severity, the severity will be reported as the most severe recording for that AE.

SAEs and pregnancy occurrences will be evaluated separately, and a narrative will be given.

AESIs will be listed. No narratives will be given.

AEs leading to withdrawal from trial or permanent discontinuation of IMP will be listed. The detailed listing will provide an overview of the individual cases and include the age and sex of the subject, if the subject was on treatment with IMP at the time of AE onset, the AE preferred and reported terms, causality and severity of the AE, the action taken with the IMP, AE outcome, start and stop date of AE, duration of AE, and number of days since first and last IMP administration. No narratives will be given.

AEs will be summarised by treatment status (on/off treatment) at the time of onset. Treatment status will be derived from IGA-CHE data..

Other events (medication error, misuse, and abuse of IMP) will be tabulated and listed. No narratives will be given.

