- 8. AEs occurring at or prior to baseline visit in this extension trial should be recorded in the parent trial. If ongoing at baseline visit for this extension trial, the AE will be recorded as medical history in the extension trial.
- 9. If the subject has IGA-CHE ≥2, delgocitinib 20 mg/g will be dispensed.
- 10. Before the first application of delgocitinib cream 20 mg/g and each time treatment is re-initiated, the subject will be instructed on how much cream to apply and which area(s) to treat.
- 11. If the subject has IGA-CHE ≥2, subject will apply delgocitinib cream 20 mg/g twice daily until IGA-CHE 0 (clear) or 1 (almost clear) is achieved.
- 12. Treatment application (yes/no) will be recorded daily by the subject in the eDiary from Day 1 onwards up to end of treatment/early termination.
- 13. All returned, opened delgocitinib cream 20 mg/g tubes will be weighed at site. Subjects must return all previously dispensed tubes of delgocitinib cream 20 mg/g to the site at all visits (scheduled and unscheduled).
- 14. HESD eDiary data from the parent trial starting from 1 week prior to and until Day 1 (baseline) in this extension trial will be transferred and considered as data for this extension trial.
- 15. While on treatment with delgocitinib cream 20 mg/g, local tolerability will be evaluated daily by the subject in the eDiary.
- 16. Subjects do not have to be fasting for safety laboratory samples.
- 17. For women of childbearing potential, a urine pregnancy test must be performed at each scheduled visit.
- 18. It will be at the investigator's discretion to decide whether a urine sample should be sent to the central laboratory for further analysis.
- 19. Only to be performed if the subject is on treatment with delgocitinib cream 20 mg/g.
- 20. Only applicable if the subject is on treatment with delgocitinib cream 20 mg/g and if the investigator suspects contact dermatitis based on the initial inspection of the subject's hands and the subject's assessment of local tolerability (Section 11.5.4).

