	
 
Reduction of HESD score, HESD itch score, and HESD pain score, (weekly averages) of ≥4 points from parent baseline at each nominal week from baseline up to Week 36.
 

	Health-related quality of life
	
 
HEIS score at each scheduled visit with assessment from baseline up to Week 36.
 

	
 
HEIS (each individual domain) score at each scheduled visit with assessment from baseline up to Week 36.
 

	
 
DLQI score at each scheduled visit with assessment from baseline up to Week 36.
 

	
 
EQ-5D-5L visual analogue score at each scheduled visit with assessment from baseline up to Week 36.
 

	
 
EQ-5D-5L index score at each scheduled visit with assessment from baseline up to Week 36.
 

	
 
WPAI:CHE domain scores at each scheduled visit with assessment from baseline up to Week 36.
 

	Exposure and treatment compliance
	
 
Total amount of delgocitinib cream 20 mg/g used during the trial.
 

	Percentage of missed applications.

- 1. In the derivation of HECSI-75 and HECSI-90 the baseline score from the parent trials will be used.
- 2. An on-treatment period is defined from the day treatment is re-initiated (when IGA-CHE score ≥2 is observed by the investigator) to the day treatment is stopped (when IGA-CHE score of 0 [clear] or 1 [almost clear] is observed by the investigator).
- 3. Number of response days (days when a subject is not on treatment with delgocitinib cream 20 mg/g) divided by number of days between baseline and end of trial.

Page 33 of 121

4. Response days are defined as the sum of days where the subject is in response periods. A response period is defined as the period from the day IGA-CHE score of 0 (clear) or 1 (almost clear) is observed by the investigator, to the day IGA-CHE score ≥2 is observed by the investigator.

5. Among subjects with a parent baseline HESD score, HESD itch score, and HESD pain score (weekly averages) ≥4 points, respectively

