#### Follow-up period (Week 36 to Week 38)

All subjects will complete a 2-week off-treatment follow-up period for the assessment of safety. The safety follow-up period will start after the Week 36 visit (end-of-treatment). Note that for subjects who permanently discontinue delgocitinib cream 20 mg/g, the 2-week follow-up period will start at the time of the early termination visit.

The safety follow-up visit will be performed via phone, but can be a site visit if needed.

Serious AEs (SAEs) will be followed up until a final outcome is established as described in Section 13.7.

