# 11.5.4.1 IMP patch test procedure

Only if the investigator suspects a local skin reaction related to application of the IMP, an IMP patch test will be performed following scoring according to the Berger and Bowman scales described in Section 11.5.4. The subject's own dispensed delgocitinib cream 20 mg/g as well

Page 63 of 121

as cream vehicle control will be used for the patch test. To avoid contamination, approximately 1 cm of delgocitinib cream should be squeezed out of the tube before performing the IMP patch test. If this is not possible, a new tube of delgocitinib cream will be used (dispensed at the given visit) for the procedure. The trial site staff will apply a small amount of delgocitinib cream and vehicle control to the patch test chambers which will be placed on the subject's upper back and secured with hypoallergenic tape. The patch will be removed after 2 days. The investigator will perform two readings of any apparent patch test reaction 3-4 days and again 5-7 days after applying the patch. The positive patch test reaction will be documented by photography and scored (Panel 15) according to guidelines (39). If the subject has a positive reaction to the IMP patch test, the subject must discontinue treatment with IMP.

Further instructions for the IMP patch test procedure, scoring of the IMP patch test reactions, and photographing any positive patch test reactions will be provided in the laboratory manual.

Panel 15: Patch test reading criteria

Morphology	Patch test reaction score
No reaction	Negative reaction
Faint erythema only	Doubtful reaction
Erythema, infiltration, possibly papules	Weak positive reaction
Erythema, infiltration, papules, vesicles	Strong positive reaction
Intense erythema, infiltrate, coalescing vesicles	Extreme positive reaction
Various morphologies, e.g. soap effect, bulla, necrosis	Irritant reaction

Reading criteria for patch test reactions based on morphology, from Johansen et al. (39).

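### The on/off-treatment AE summary has no carry-over days, so cream-related reactions that start after a stop are counted as off-treatment

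*Combined protocol and SAP*

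**What the plan says.** Section 14.3.8.1 plans a supplementary AE summary: "AEs will be summarised by treatment status (on/off treatment) at the time of onset". It adds: "Treatment status will be derived from IGA-CHE data". Panel 3 in Section 6 gives the boundaries. An on-treatment period runs "to the day treatment is stopped (when IGA-CHE score of 0 [clear] or 1 [almost clear] is observed by the investigator". The complementary state starts on that same day: "A response period is defined as the period from the day IGA-CHE score of 0 (clear) or 1 (almost clear) is observed". No section adds a lag, carry-over or washout to the split.

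Three other places bear on timing after contact:

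- In the IMP patch test (Section 11.5.4.1) the patch comes off after 2 days, and the investigator makes "two readings of any apparent patch test reaction 3-4 days and again 5-7 days after applying the patch".
- Section 7.1 ends the trial with a safety window: "All subjects will complete a 2-week off-treatment follow-up period for the assessment of safety".
- The investigator's local tolerability assessment (Panel 2, footnote 19) is "Only to be performed if the subject is on treatment with delgocitinib cream 20 mg/g".

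**The concern.** Sensitisation, allergic and irritant contact dermatitis, local immunosuppression and skin infection are the local risks named in Section 5.5. If any of these starts only after the last application, the split places it in the off-treatment column although the cream caused it. Each such event leaves the on column and enters the off column, so the contrast shrinks toward no difference. In a trial whose primary objective is safety, that is the unhelpful direction.

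The end of the trial has a 2-week follow-up, but the analysis gives earlier stops nothing equivalent, and a subject can have several. The clearest case is Day 1. Under Sections 7.1 and 9.3.1, subjects with IGA-CHE 0 or 1 at baseline are taken off treatment. Those who had delgocitinib have just finished 16 weeks of twice-daily use, and a reaction on Day 3 would be filed as off-treatment. The problem would remain even if every stop were dated correctly and the rate denominators were right.

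**Working it through.** **1. Carry-over in the plan.** Status is read at onset, and the on-treatment period ends on the stop day, so the carry-over is 0 days. The stop day itself belongs to both Panel 3 periods, so an event starting that day has no defined column.

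**2. Timings elsewhere in the protocol.**

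- Patch readings relative to removal: 3 − 2 = 1 day to 7 − 2 = 5 days.
- Final follow-up (Panel 2): Day 267 − Day 253 = 14 days.

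These show that safety events are looked for after contact ends. They do not give a latency after a course of cream on the hands.

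**3. Illustration A: delayed onset.** The documents give no course lengths, latencies or AE rates, so all three are assumed. If reactions are caused evenly over a course of D days and appear L days later, the share with onset after the stop is L/D.

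| L | D = 28 | D = 56 | D = 112 |
|---|---|---|---|
| 3 days | 10.7% | 5.4% | 2.7% |
| 7 days | 25.0% | 12.5% | 6.25% |

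To express this as rates, assume a background of 100 and cream-caused events of 40 per 100 person-years on treatment (true ratio 140/100 = 1.40), with S days off after each course.

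- Observed on rate = 100 + 40 × (D − L)/D. Observed off rate = 100 + 40 × L/S.
- D = 28, S = 28, L = 7: 130 against 110, ratio 1.18.
- D = 112, S = 56, L = 7: 137.5 against 105, ratio 1.31.

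**4. Illustration B: persisting risk.** Suppose instead that the on rate is twice the off rate and stays at that level for w days after a stop, with off periods of S days. The on rate is then unchanged and only the off rate rises: ratio = 2/(1 + w/S).

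| w | S = 28 | S = 56 | S = 112 |
|---|---|---|---|
| 5 days | 1.70 | 1.84 | 1.91 |
| 7 days | 1.60 | 1.78 | 1.88 |
| 14 days | 1.33 | 1.60 | 1.78 |

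**5. What a separate category shows.** Take the first case in step 3 (D = 28, S = 28, L = 7).

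- A 7-day post-stop category has rate (100 × 7 + 40 × 7)/7 = 140, and later off time has 100.
- A 14-day category has (100 × 14 + 40 × 7)/14 = 120, and later off time again has 100.
- Merging 7 days into the on column gives (100 × 35 + 40 × 28)/35 = 132, ratio 1.32.

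The separate category recovers the clean off rate and leaves the attribution open. Merging also cleans the off rate, but it dilutes the on rate.

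**The case against.** A reader might infer that the protocol itself expects reactions days after contact. It does not say so. The patch test is a diagnostic provocation under occlusion on the back, read on a guideline schedule. The 2-week follow-up is a general safety period, and Section 5.5 lists local risks without timing. The documents allow for delayed reactions and go no further.

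A reader might also take the 1.33 in illustration B as the likely distortion. It needs the full doubled rate, across all AEs, to persist for 14 days. With the 5 days that the patch timing suggests, the range is 1.70 to 1.91.

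Nor is off-treatment time the only internal reference. Section 14.3.12 also presents data by parent-trial treatment and baseline IGA-CHE status. Section 14.1 plans no comparative analyses, and on/off is confounded with disease state by design, since on means IGA-CHE 2 or more and off means 0 or 1. A lag category would not turn the split into an estimate of drug effect.

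Finally, events are not lost. All AEs with onset after baseline are treatment-emergent whatever the status, causality is assessed and tabulated, and AEs are collected at every visit. A visit at which treatment is stopped includes AE collection and the tolerability assessment. The listing of AEs leading to discontinuation or withdrawal gives days since last administration.

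All of this stands and limits the point to one descriptive table. It does not answer the point: the stop-visit check precedes the days in question, and nothing else in the plan separates those days in the on/off table. Section 14.3.12 mentions a statistical analysis plan that could define a window, but no such text appears in the document.

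**Conclusion.** The point holds as a limited one. With 0 carry-over days, any cream-related reaction with onset after a stop is counted as off-treatment, and the on/off summary is pulled toward no difference. The direction follows from the rule, provided that some cream-caused events start late. The size cannot be computed from the documents. The range of about 3% to 25% misplaced, and the ratios in the working, rest wholly on assumed latencies, course lengths, off periods and rates. Short courses and short off periods make it worse. The primary endpoint, overall AE tables and related-AE tables are unaffected, so the documents do not support reading this as a flaw in the trial's main safety result. A cheap supplementary display is a proportionate response.

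**What to change.** Keep the IGA-CHE-based on/off summary in Section 14.3.8.1, which Amendment 3 chose so that AE allocation matches the on-treatment definition. Add a supplementary display of events and person-time by state at onset:

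- on treatment;
- post-stop, for example 1-14 days after the last application of a course, with 7 days as a sensitivity;
- later off-treatment time;
- time not yet exposed to delgocitinib, such as former vehicle subjects who are off treatment from Day 1.

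Use the first and last application dates that the eCRF records at each start and stop (Section 9.8.4, reporting in eCRF). Put the early post-baseline days of former delgocitinib subjects taken off on Day 1 in the post-stop category, counted from the baseline visit if the last parent-trial application date is not available. State which column takes the stop day in the planned summary.

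The cost is SAP wording and one extra table, with no new data from courses in this trial and no change to treatment or visits. The downsides are smaller cells and a window length that is a convention. Because the window is shown separately, a reader can add it to either side.

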# 14.3.8.2 Vital signs and physical examination

For vital signs (resting blood pressure, pulse, and body temperature), the absolute values at baseline and Week 8, 16, 24, and 36 as well as the changes from baseline to Week 8, 16, 24, and 36 will be summarised as mean, standard deviation (SD), median, minimum, and maximum values.

Subjects with abnormal, clinically significant physical findings will be listed.

## 14.3.8.3 Clinical laboratory evaluation

For laboratory parameters, the absolute values at baseline and Week 8, 16, 24, and 36 as well as the changes from baseline to Week 8, 16, 24, and 36 will be summarised as mean, SD, median, minimum, and maximum values.

For selected liver, kidney, lipid, and haematology parameters, guideline or literature-defined thresholds will be used for producing shift tables and categorical threshold tables. The remaining laboratory parameters will be classified as 'low', 'normal', or 'high', depending on whether the value is below, within, or above the reference range and these categories will be used for producing shift tables. Shift tables will be either from baseline to end-of-treatment,

Page 86 of 121

from baseline to maximum post-baseline value, or from baseline to minimum post-baseline value.

Subjects with laboratory parameters outside the reference range will be listed.

## 14.3.9 Subject assessment of local tolerability

Subject assessment of local tolerability will be summarised by nominal week.

## 14.3.10 Interim analysis

No interim analysis is planned.

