#### 14 Statistical methods

## 14.1 Sample size

The expected sample size for this trial is approximately 600 subjects. No formal sample size has been calculated, as the primary objective for the trial is to evaluate safety, which is reflected by the open-label trial design. No comparative analyses are performed in this trial. The expected sample size is based on the population size of the parent trials (920 subjects) and assumptions regarding completion rates in the parent trials.

The aim is to have sufficient exposure for an adequate safety evaluation of long-term treatment according to the ICH E1 guideline. The target is a minimum of 300 subjects completing 6 months and 100 subjects completing 12 months of treatment with delgocitinib, respectively. Six months of treatment is defined as 16 weeks of twice-daily delgocitinib cream 20 mg/g plus 10 weeks with twice-daily delgocitinib cream 20 mg/g as needed treatment, or cream vehicle (in the parent trial) plus 26 weeks with twice-daily delgocitinib cream 20 mg/g as needed treatment. Similarly, 12 months of treatment is defined as 16 weeks of twice-daily delgocitinib cream 20 mg/g as needed treatment.

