# 14.3.5 Analysis of secondary endpoints

The analysis of the secondary endpoints will be based on the safety analysis set.

IGA-CHE and HECSI scores will be summarised at each scheduled visit from baseline up to Week 36 based on observed data.

In addition, the proportion of the subjects achieving IGA-CHE score of 0 (clear) or 1 (almost clear), HECSI-75 and HECSI-90 will be summarised at each scheduled visit from baseline up to Week 36, where subjects who discontinue treatment with IMP prior to Week 36, initiate rescue treatment, or withdraw from the trial, whichever comes first, will be imputed as non-responders.

In the derivation of HECSI-75 and HECSI-90 the baseline score from the parent trials will be used.

THIS DOCUMENT CONTAINS CONFIDENTIAL INFORMATION AND MUST NOT BE COPIED OR MADE AVAILABLE TO ANY THIRD PARTY WITHOUT THE PRIOR WRITTEN CONSENT OF THE LEO PHARMA GROUP

Trial ID: LP0133-1403 Date: 03-Apr-2023

Page 83 of 121

Version: 4.0, Final

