# 14.3.11 Analysis of data to support submission for marketing authorisation approval

To support submission for marketing approval, analyses of data will be performed once sufficient exposure (defined in section 14.1) is available to evaluate the long-term safety of delgocitinib cream 20 mg/g. Results of these analyses will be included in a preliminary clinical trial report.

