# 14.3.12 General principles

If nothing else is stated, an observed-cases approach will be used for tabulations of data by visit (that is, involving only those subjects who attended each specific visit).

Baseline measurements will be defined as the latest available observation at or prior to the baseline visit (Day 1), unless otherwise specified (e.g. baseline of the parent trial will be used for responder's definition of HECSI-75/90).

Categorical data will be summarised using the number and percentage of subjects in each category. Continuous data will be summarised using the mean, median, quartiles, SD, minimum, and maximum values.

Data will be presented for the total cohort of subjects, as well as the combination between randomised treatment in the parent trial (delgocitinib 20 mg/g or cream vehicle) and IGA-CHE TS status at baseline (IGA-CHE 0/1 or  $\ge 2$ ), when appropriate.

Any changes from the statistical analyses planned in this clinical trial protocol will be described and justified in a protocol amendment, the statistical analysis plan, and/or in the CTR, depending on the type of change.

Page 87 of 121

All statistical analysis will be based on the safety analysis set.

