#### **Data handling**

Data will be collected by means of electronic data capture unless transmitted electronically to LEO Pharma or designee (e.g. laboratory data). The investigator or staff authorised by the investigator will enter subject data into an electronic CRF (eCRF). Data recorded in the eCRF will be accessible to the trial site and LEO Pharma personnel immediately after entry. The eCRF must be maintained in an up-to-date state by the trial site at all times.

The investigator must verify the correctness of the data entered by the site by electronically dating and signing the eCRF. This signature information will be kept in the audit trail and cannot be altered. Any correction(s) made by the investigator or authorised site staff to the eCRF after original entry will be documented in the audit trail. Changes to data already approved will require re-signature by the investigator. The person making the change to the data, and the date, time, and reason for the change will be identified in the audit trail.

Subject data should be entered into the eCRF no later than 5 working days after each visit, unless a different deadline is stated in the clinical trial agreement. Queries for discrepant data will be generated automatically by the system upon entry or manually by the CRA, sponsor's medical expert, or the data manager. All queries will be raised electronically within the electronic data capture system. This systematic validation will ensure that a clean and consistent database is provided for the statistical analysis.

An electronic PRO (ePRO) solution will be used to capture patient-reported data (data from questionnaires completed at the trial site and eDiary data). By the use of an ePRO, data will be available immediately after data entry and available for CRAs and site personnel, including the investigator, with reader access only. The ePRO system is a separate application from the eCRF and data captured from the eCRF and the ePRO will be stored on different servers during data capture. Data from both systems will be included in the final trial database.

Page 102 of 121

External data transfers from vendors to LEO Pharma will be transmitted and handled via a secure file transfer protocol site.

During the conduct of the study, 2 database locks will be performed to support submission for marketing approval.

Transmissions of data are documented in more detail in the data flow plan which is part of the trial master file.

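### Section 14.3.10 rules out an interim analysis that 14.3.11 then schedules; with no due-visit rule, responder tables made at that cut would understate late-visit response by about 1 to 10 points

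*Combined protocol and SAP*

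**What the plan says.** Section 14.3.10 consists of one statement: "No interim analysis is planned". The next section, 14.3.11, says that "analyses of data will be performed once sufficient exposure (defined in section 14.1) is available to evaluate the long-term safety" of the product, and adds: "Results of these analyses will be included in a preliminary clinical trial report". Appendix 3D, under data handling, says: "During the conduct of the study, 2 database locks will be performed to support submission for marketing approval".

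The trigger is in 14.1: "The target is a minimum of 300 subjects completing 6 months and 100 subjects completing 12 months of treatment with delgocitinib, respectively". About 600 subjects are expected, and no comparative analyses are planned.

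For IGA-CHE 0/1, HECSI-75 and HECSI-90 at each scheduled visit up to Week 36, section 14.3.5 says that subjects who stop the product early, start rescue or withdraw, "whichever comes first, will be imputed as non-responders". Section 14.3.7 applies the same rule to the HESD reduction of at least 4 points at each nominal week, and 14.3.13 states it for binary responses generally, leaving all other missing values unimputed. Section 14.3.12 adds that, unless stated otherwise, "an observed-cases approach will be used for tabulations of data by visit".

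**The concern.** Analysing accumulating data before the trial ends, and reporting it, is an interim analysis in the ordinary sense. Because 14.3.10 does not acknowledge it, the plan never sets out what such a cut needs: a cut-off date, a list of tables, the purpose of each lock, and a rule for visits that some subjects have not yet reached.

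The last gap affects a result. Take two subjects enrolled on the same day, both at Week 12 when the database is cut. One stopped treatment at Week 4 and, under the imputation rule as written, is already a Week 36 non-responder. The other is still in the trial, has no Week 36 value, and is not in the Week 36 table. Failures are drawn from everyone enrolled and successes only from those enrolled early enough. The distortion grows with visit week, because fewer subjects are due at later visits, so response would seem to fade over time and then recover at the final lock. In a report supporting a marketing submission, that would be an artefact in the long-term efficacy data, which are the trial's secondary objective.

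**Working it through.** The plan gives no response, discontinuation or enrolment figure, so there is no stated figure to reproduce. The direction follows from the rule alone; the size needs assumptions.

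**Formula.** At the cut, let M be the subjects whose Week 36 date has passed, d the share who discontinue by Week 36, r the response among those observed, and D the subjects who have discontinued but whose Week 36 date has not come.

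- Due visits only: r(1 - d).
- Rule as written: M(1 - d)r / (M + D).
- Ratio: M/(M + D). This is below 1 whenever D > 0, and equals 1 in the final data, where D = 0.

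**Check 1: simple cut.** From 14.1: 600 subjects. Assumed: r = 60%; a share q of subjects past Week 36; the rest spread evenly over Weeks 0 to 36 with discontinuation accruing linearly, so on average d/2 of them have stopped. Then M = 600q and D = 600(1 - q)d/2.

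| d | q | M | D | Due visits only | As written | Difference |
|---|---|---|---|---|---|---|
| 15% | 0.5 | 300 | 22.5 | 153/300 = 51.0% | 153/322.5 = 47.4% | 3.6 |
| 15% | 0.3 | 180 | 31.5 | 91.8/180 = 51.0% | 91.8/211.5 = 43.4% | 7.6 |
| 20% | 0.3 | 180 | 42 | 86.4/180 = 48.0% | 86.4/222 = 38.9% | 9.1 |
| 10% | 0.7 | 420 | 9 | 226.8/420 = 54.0% | 226.8/429 = 52.9% | 1.1 |

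**Check 2: cut tied to the exposure target.** Assumed: the cut falls when 100 subjects from the parent active arm complete Week 36; uniform enrolment over 26, 52 or 78 weeks; constant discontinuation hazard with d from 5% to 30%; r = 50%; half or two thirds of rollovers from the parent active arm. Twelve months is taken as 16 + 36 = 52 weeks. This too is an assumption, because the 12-month definition in 14.1 mentions only 16 weeks and reads as incomplete.

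- Two thirds active, 52-week enrolment, d = 10%: M = 167 (150 observed, 75 responders), D = 21. 75/167 = 45.0% (M unrounded) against 75/188 = 39.9%, a difference of 5.1 points.
- Same with d = 20%: M = 188, D = 43. 40.0% against 32.5%, a difference of 7.5 points.
- Smallest in the grid (half active, 78 weeks, d = 5%): M = 211, D = 7. 47.5% against 46.0%, a difference of 1.5 points.
- Largest (two thirds active, 26 weeks, d = 30%): M = 214, D = 92. 35.0% against 24.5%, a difference of 10.5 points.

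**Does the 6-month condition delay the cut?** Not in the first example, where the cut falls at week 50. Of 400 parent-active subjects, 400 × 40/52 = 308 enrolled at least 10 weeks earlier. Of 200 parent-vehicle subjects, 200 × 24/52 = 92 enrolled at least 26 weeks earlier. The total is 400. Removing a full 10% leaves 360, above the required 300.

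**Alternative denominator.** Dividing by all subjects enrolled at the cut does not rescue the figure: in the first example of check 2 it gives 75/582 = 12.9%.

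**The case against.** The strongest reply has four parts.

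**The conflict is mostly one of label.** Section 14.3.11 openly discloses the early analyses, their purpose and their output, and Appendix 3D agrees with it. In an open-label trial with no comparative analyses, 14.3.10 can be read as ruling out only a look that could stop or alter the trial. This largely stands. A reader might infer a concealed interim look that spends alpha, but there is no hypothesis test to spend it on. Relabelling alone changes no result.

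**The plan is not silent on timing.** Section 14.1 supplies an exposure trigger. That stands as well. What is missing is narrower: a cut-off date and a due-visit condition.

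**The preliminary report may hold no responder tables.** Section 14.3.11 describes its analyses as serving the evaluation of long-term safety. A reader might infer that the efficacy results in the submission will be biased. The document does not say so, because it never lists the tables in that report. It does not limit them to safety either, so the point is conditional.

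**A visit not yet due is arguably not a missing value**, and a careful programmer would leave it out. That is sensible practice, but the text does not require it. Sections 14.3.5 and 14.3.7 attach the rule to every visit or nominal week up to Week 36 with no date limit. Section 14.3.12 asks that changes to planned analyses be described and justified, and allows this in a statistical analysis plan. A due-visit condition could be written there, but none appears in the document reviewed.

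**Conclusion.** The point holds in conditional form. The three passages on early analysis need reconciling. If responder tables are produced at a cut before trial end under the rule as written, late-visit response is understated by the factor M/(M + D). The direction needs no assumption about response; it needs only some discontinuers whose visit is not yet due. The size rests on assumed enrolment, discontinuation of 5-30% and response of 50-60%. Across the two checks it is 1.1 to 10.5 points at Week 36, so about 1 to 10.

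A reader might arrive at a larger figure by charging subjects not yet due with the full 36-week discontinuation. With d = 15% and q = 0.5 that makes D = 300 × 0.15 = 45 and gives 153/345 = 44.3%. With d = 20% and q = 0.3 it makes D = 420 × 0.20 = 84 and gives 86.4/264 = 32.7%, which is 15.3 points below 48.0%. Those figures are not supported, because later enrollees have had less time to discontinue.

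The adverse-event primary endpoint, the observed-case IGA-CHE and HECSI score summaries, and the final analysis are not affected.

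**What to change.** 1. In 14.3.10, state that the analyses in 14.3.11 are descriptive analyses at planned data cuts, with no stopping or design decision attached.
2. In 14.3.11, define the data cut-off for each of the two locks in Appendix 3D, and say which tables the preliminary report will contain.
3. In 14.3.5, 14.3.7 and 14.3.13, add that at any lock before trial end a subject enters a visit's or nominal week's denominator, whether observed or imputed, only if its nominal date is on or before the cut-off.

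The cost is a few sentences and one date condition in the programs. Late-visit denominators in the preliminary report become smaller: in the first example of check 2, 167 instead of 188 at Week 36. No visit, treatment or data collection changes, and the final tables stay the same.
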